7.1.1 Serious Adverse Event (SAE) Definitions

An AE that (related or not related to the investigational test articles, comparator products or study procedures):

• Led to death

- Led to serious deterioration in the health of the subject, that resulted in:
 - A life-threatening illness or injury; or
 - A permanent impairment of a body structure or a body function (e.g., blindness); or
 - Inpatient or prolonged hospitalization; or
 - Medical or surgical intervention to prevent life-threatening illness or injury or permanent impairment to a body structure or a body function
- Led to fetal distress, fetal death, or a congenital abnormality or birth defect.

Note: A planned hospitalization for a pre-existing condition, or a procedure required by the protocol, without serious deterioration in health, is not considered an SAE.

Serious adverse events may include but are not limited to any hazardous, sight-threatening conditions occurring after exposure to the investigational test article or control product including, but not limited to, the following:

- A presumed infectious ulcer (defined as a progressive erosion of the corneal tissue). For the purposes of reporting, this includes:
 - Central or para-central location
 - Penetration of Bowman's membrane
 - Infiltrate $\geq 2 \text{ mm diameter}$
 - Associated with iritis
 - Associated with any increase in intraocular pressure
 - Culture positive for microorganisms
 - Increasing size or severity at subsequent visits

NOTE: Signs of a presumed infectious corneal ulcer may include irregular focal infiltrates, active lesions with raised edges, significant diffuse infiltration, anterior corneal to mid-stromal involvement, erosion with overlying staining, conjunctival and lid edema, anterior chamber reaction (iritis), and severe bulbar and limbal redness. Symptoms associated with a presumed infectious ulcer (microbial keratitis) may include pain of rapid onset, severe redness, purulent or mucopurulent discharge, tearing, and photophobia.

- Any central or paracentral (within the central 6 mm of cornea) corneal event that results in permanent opacification (such as corneal scar or vascularization)
- Any serious adverse ophthalmic events including hypopyon and/or hyphema
- Any neovascularization within the central 6 mm of the cornea
- Permanent loss of ≥ 2 lines of BSCVA
- All cases of iritis.

7.1.2 Significant Non-Serious Adverse Event Definitions

A significant non-serious adverse event is an AE that does not meet the serious criteria, is considered significant by the Sponsor, and requires expedited reporting to the Sponsor (see Section 7.2.1.). These events include but are not limited to:

- Peripheral non-progressive non-infectious corneal ulcers
- All symptomatic corneal infiltrative events
- All cases of corneal staining greater than or equal to Grade 3
- A temporary loss of two or more lines of BSCVA (for greater than or equal to 2 weeks)
- Neovascularization cases Grade 2 or greater (if not within 6 mm of the cornea)
- Any ocular event that necessitates temporary lens discontinuation of greater than or equal to 2 weeks.

7.1.3 Non-Significant Non-Serious Adverse Events Definitions

A non-significant non-serious adverse event may include but are not limited to the following and does not require expedited reporting:

- Bacterial Conjunctivitis;
- Viral Conjunctivitis;
- Allergic Conjunctivitis;
- Corneal Edema;
- Contact Lens Related Papillary Conjunctivitis; and
- Loss of Contrast Sensitivity.

7.1.4 Adverse Device Effect (ADE) Definitions

An adverse device effect (ADE) is an AE that is assessed to be related to the use of an investigational medical device. This definition includes AEs resulting from insufficient or inadequate instructions for use; deployment, implantation, installation, or operation; or any malfunction of the investigational medical device. This definition also includes any event resulting from use error or from intentional misuse of the investigational medical device.

7.1.4.1 Anticipated Serious Adverse Device Effect (ASADE) Definition

An anticipated serious adverse device effect (ASADE) is an ADE that first meets the serious criteria (see Section 7.1.1) and which, by its nature, incidence, severity or outcome, has been previously identified in the investigational plan or application (including a supplementary plan or application) and/or in the risk analysis report. ASADEs include but are not limited to:

- Corneal Ulcer (infectious or non-infectious)
- Keratitis
- Sensitivity to light (photophobia)
- Excessive eye secretions including mucopurulent discharge
- Blurred vision, rainbows or halos around objects
- Poor visual acuity (reduced sharpness of vision)
- Moderate to severe eye pain not relieved by removing the lens

7.1.4.2 Unanticipated Serious Adverse Device Effect (USADE) Definitions

An unanticipated serious ocular or non-ocular adverse device effect (USADE) is an adverse event related to the use of an investigational medical device that has resulted in any of the consequences characteristic of a serious adverse event as described in section 7.1.1 and

Study #914 - Protocol

which by its nature, incidence, severity or outcome has not been identified in the current version of the risk analysis report.

This definition includes but is not limited to AEs resulting from insufficient or inadequate instructions for use, deployment, implantation, installation, or operation, or any malfunction of the investigational medical device.

This definition also includes any event resulting from use error or from intentional misuse of the investigational medical device. USADEs include but are not limited to:

- Any central or paracentral (within 6 mm of cornea) corneal event that results in permanent opacification (such as corneal scar or vascularization)
- Any serious adverse ophthalmic events including hypopyon and/or hyphema
- Any neovascularization within the central 6 mm of the cornea
- Permanent loss of ≥ 2 lines of BSCVA
- All cases of iritis.

7.1.5 Relationship Definition: Study Device and/or Other Study Materials

- **Related:** There is at least a reasonable possibility that the AE is related to the study device (study solution) and/or rewetting drops. Reasonable possibility means that there is evidence to suggest a causal relationship or association between the study device and/or rewetting drops and the AE.
- Not related: There is little or no reasonable possibility that the AE is related to the study device (study solution) and/or rewetting drops. This assessment implies that the AE has no evidence to suggest either a causal relationship or association to the study device and/or rewetting drops and a more likely or certain alternative etiology exists.

7.1.6 Severity Definitions

- **Mild:** Subject awareness of a sign or symptom that is easily tolerated, requires no treatment, and does not interfere with subject's daily activities.
- **Moderate:** Subject awareness of a sign or symptom which may be a low level of concern to the subject and may interfere with daily activities but can be relieved by simple therapeutic care.
- Severe: A sign or symptom that interrupts the subject's daily activity and requires systemic therapy or other treatment

7.2 **Procedures for Evaluating Adverse Events**

Throughout the course of this study all efforts will be made to remain alert to reportable AEs. If an AE occurs the first concern will be the safety of the subject and appropriate medical intervention will be made. All SAEs, ocular and systemic, must be recorded and reported as required.

All reportable AEs occurring after signing of informed consent and through the subject's end of participation in the study must be reported. All reportable AEs must be followed until the event resolves or stabilizes. This may imply that follow-up will continue after the subject has left the study, and that additional evaluations may be requested by the Sponsor.

Ocular AEs of possible clinical significance should be photo-documented and shared with the Medical Monitor in electronic form.

[figure not shown]
When evaluating for reportable AEs, the Investigator should refer to the definitions for AEs to determine:

- a) whether the event is serious (refer to Section 7.1.1 and 7.1.2.)
- b) whether the event is severe (refer to Section 7.1.6.)
- c) whether the event is significant (refer to Sections 7.1.2 and 7.1.3.)
- d) whether the event is related to the study device (refer to Section 7.1.5.)

7.2.1 **Procedures for Reporting Serious or Significant Adverse Events**

An AE classified as a SAE or a Significant Non-Serious Ocular AE requires expeditious handling and reporting to the Sponsor to comply with regulatory requirements, as follows:

- The event must be reported to the Medical Monitor (Section 24) within 24 hours of the Investigator's awareness of the event via facsimile/email transmission on a paper SAE or Significant Non-Serious AE Report Form signed by the Investigator.
- The Medical Monitor will email a copy of the form (within 24 hours) to all parties listed below:

Investigators should not wait to receive additional information to fully document the event before initially notifying the Medical Monitor of an SAE or a Significant Non-Serious AE. Additional relevant information such as hospital records and autopsy reports should be provided to the Medical Monitor as soon as they are available.

- The Investigator should take all appropriate measures to ensure the safety of the subjects: notably, he/she should follow a subject with an SAE or Significant Non-Serious AE until the event has resolved or the condition has stabilized. This may imply that follow-up will continue after the subject has left the study, and that additional evaluations may be requested by the Sponsor.
- Ensure that the subject's identity is protected and the subject's identifiers in the clinical trial are properly mentioned on the form.
- BEGIN TREATMENT OF THE AE IMMEDIATELY BY A SUITABLY LICENSED EYE CARE PROFESSIONAL.
- Continue to update the paper SAE or Significant Non-Serious AE Report Form, if applicable, each time the subject is seen during the management of the event and at resolution of the event. All updated report forms should be submitted by the site to the Medical Monitor within 24 hours. The Medical Monitor should distribute the updated reports to appropriate Sponsor personnel. Whenever

possible, it is suggested that the Investigator take photographs of all ocular AEs of possible clinical significance and forward them to the Medical Monitor.

- Events requiring medical treatment will be evaluated by the Sponsor. Upon review of the medical treatment, Bausch + Lomb Clinical Operations representatives may contact the Investigator to request further information concerning the treatment.
- Report all USADEs to the reviewing IRB within 10 working days following awareness of the USADE or according to the established reporting procedures of the IRB, whichever is shorter.
- Submit all bills, prescription receipts, and culture reports/fees related to the AE to the Bausch + Lomb Clinical Operations. Expense incurred for study related medical treatment will be paid by Bausch +Lomb Clinical Operations.

7.2.2 Procedures for Reporting Off-Site Unanticipated Serious Adverse Device Effects

When participating in multicenter clinical investigations, Investigators may receive off-site USADE reports. These are Sponsor reports of USADEs which occurred at other clinical sites for the same trial, or in different trials using the same investigational test article or comparator, that met the criteria for reporting to a regulatory agency. These should be reported to the reviewing IRB within 10 working days or per their established reporting procedures, whichever is shorter.

7.2.3 Device Deficiencies: Definition and Reporting Procedures

A device deficiency is defined as an inadequacy of a medical device with respect to its identity, quality, durability, reliability, safety, or performance. Device deficiencies include malfunctions, use errors, and inadequate labeling.

Investigators must evaluate, record, and report any complaints/ deficiencies or malfunctions experienced with the study solution during this trial to the Medical Monitor promptly. The Sponsor and Medical Monitor shall review all device deficiencies and, upon the Sponsor's request, Investigators must supply any additional information related to the safety reporting of a particular event.

Report device deficiencies within 24 hours of knowledge to:

The Medical Monitor will distribute, within 24 hours of knowledge, all device deficiencies to the Sponsor.

The Sponsor shall review all device deficiencies and determine and document in writing whether they could have led to an SAE. In the event of a disagreement between the Sponsor and the Investigator(s), the Sponsor shall communicate both opinions to the reviewing IRB per their established reporting procedures and the health authority.

7.2.4 Procedures for Culturing of Corneal Ulcer or Suspected Ocular Infection

For purposes of this study, the Sponsor requests that cultures should be obtained in cases of corneal ulcer or suspected ocular infection, unless medically contraindicated. Cultures should be taken from the cul-de-sac, lower eyelid margin, and the corneal lesion (if applicable). The required culturing techniques are outlined in Appendix B, Section 8.0).

When a culture is obtained, the contact lenses and contact lens cases which were being utilized by the subject at the time of the AE should be collected from the subject for culturing and processing by the local clinical laboratory designated by the site.

Microbial data generated from returned subject supplies (e.g., lenses, lens cases, and/or lens case solutions) are for information only. Because microbes may be introduced into subject supplies during use, recovery of microbes from returned subject supplies cannot be presumed to indicate etiology or direction of organism transmission.

The ocular cultures, along with the associated contact lenses and contact lens cases, will be sent to the local clinical laboratory designated by the site for analysis. The clinical laboratory will report the culture results to the Investigator who will record the results in the eCRF.

7.2.5 Guidelines for Reporting Pregnancies

During the study, all female subjects of childbearing potential should be instructed to contact the Investigator immediately if they suspect they might be pregnant (e.g., missed or late menstrual period). Female subjects who become pregnant during the study will be followed until completion of pregnancy. Every effort will be made to obtain the health status of the mother and infant or fetus (in cases of miscarriage or therapeutic abortion) at term. Pregnancy itself is not considered an AE.

All confirmed pregnancies must be reported on a Pregnancy Report and submitted to the Medical Monitor via facsimile or email transmission within 24 hours of the Investigator's awareness of the pregnancy. The Medical Monitor will distribute the completed report to the Sponsor as per the distribution listed below.

All pregnancies will be followed until outcome even after study closure. The outcome of all pregnancies will be reported on a paper Pregnancy Outcome Report and submitted to the Medical Monitor via facsimile or email transmission once the outcome is learned. The Medical Monitor will distribute the completed report to the Sponsor as per the distribution listed below.

Although pregnancy occurring in a clinical study is not considered to be an AE or SAE, any pregnancy complication, spontaneous abortion, or elective termination of a pregnancy, for medical reasons, will be recorded as an SAE. Any serious complication or event resulting from the pregnancy should be reported to the Medical Monitor within 24 hours on the SAE or Significant Non-Serious AE Report Form along with the Pregnancy Report Form.

The contact for reporting pregnancies and pregnancy outcomes are:

Date:19 JAN 2023 Confidential

8.0 STATISTICAL METHODS

Changes to these statistical plans that are made prior to unmasking of study treatments will be documented in protocol amendments and/or the statistical analysis plan. Changes made after unmasking will be described in the clinical study report.

8.1 Study Endpoints

8.1.1 Primary Effectiveness Endpoints

The primary effectiveness endpoints are as follows.

- a. Overall comfort averaged over all scheduled follow-up visits (Appendix B, Section 6.0, Rating Scale #3)
- b. Vision averaged over all scheduled follow-up visits (Appendix B, Section 6.0, Rating Scale #12)
- c. The proportion of eyes with a maximum degree of front surface deposits grade of ≤ 2 over all scheduled follow-up visits.

8.1.2 Secondary Effectiveness Endpoints

There are no predefined secondary effectiveness endpoints.

8.1.3 Supportive Effectiveness

The supportive effectiveness outcomes are the percentages of subjects agreeing with the consumer survey statements.

8.1.4 Primary Safety Endpoint

The primary safety endpoint is the proportion of eyes with any slit-lamp findings greater than Grade 2 over all follow-up visits.

8.2 Hypotheses

The noninferiority margins that follow are commonly used values in the industry for the corresponding endpoints. The study will be statistically successful if the Test lens is statistically successful in all primary endpoints.

8.2.1 Overall Comfort Averaged Over All Follow-up Visits

The null hypothesis (H_0) is that the difference in mean overall comfort (test group mean $[\mu_T]$ minus standard group mean $[\mu_S]$) is less than or equal to negative five points. The alternative hypothesis (H_1) is that the difference is greater than negative five points.

$$H_0: \mu_T - \mu_S \le -5$$

 $H_1: \mu_T - \mu_S > -5$

8.2.2 Vision Averaged Over All Follow-up Visits

The null hypothesis (H_0) is that the difference in mean vision score (test group mean [μ_T]

Date:19 JAN 2023 Confidential minus standard group mean $[\mu_S]$ is less than or equal to negative five points. The alternative hypothesis (H_1) is that the difference is greater than negative five points.

$$H_0: \mu_T - \mu_S \le -5$$
$$H_1: \mu_T - \mu_S > -5$$

8.2.3 Front Surface Deposits at All Follow-up Visits

The null hypothesis (H_0) is that the difference in the proportion of eyes with maximum front surface deposits grade of ≤ 2 at all Follow-up Visits (test group proportion [π_T] minus standard group proportion [π_S]) is less than or equal to -0.1 (-10%). The alternative hypothesis (H_1) is that the difference is greater than -0.1 (-10%).

$$H_0: \pi_T - \pi_S \le -0.1$$
$$H_1: \pi_T - \pi_S > -0.1$$

8.2.4 Slit-Lamp Findings Greater than Grade 2

The null hypothesis (H_0) is that the difference in the proportion of eyes with slit-lamp findings greater than grade 2 (test group proportion [π_T] minus standard group proportion [π_S]) is greater than or equal to 0.05 (5%). The alternative hypothesis (H_1) is that the difference is less than 0.05 (5%).

$$H_0: \pi_T - \pi_S \ge 0.05$$

 $H_1: \pi_T - \pi_S < 0.05$

8.2.5 Subject Assessments

Each of the following hypotheses will be evaluated for each of twelve statements in the Subject Assessment Questionnaire.

8.2.5.1 **Proportion of Test Group Respondents Agreeing**

The null hypothesis (H_0) is that the proportion of respondents in the Test group agreeing with the statement (π_T) is less than or equal to 0.5. The alternative hypothesis (H_1) is that the proportion agreeing is less than 0.5.

$$H_0: \pi_T \le 0.5$$

 $H_1: \pi_T > 0.5$

8.2.5.2 Comparison Between Groups of the Proportion of Respondents Agreeing

The null hypothesis (H_0) is that the proportion of respondents in the Test group agreeing with the statement (π_T) is less than or equal to the proportion of respondents in the Control group (π_T). The alternative hypothesis (H_1) is that the proportion agreeing in the Test group is greater than the proportion agreeing in the Control group.

$$H_0: \pi_T \le \pi_C$$
$$H_1: \pi_T > \pi_C$$

8.3 Sample Size

Estimates of standard deviations and proportions were obtained from Bausch + Lomb Study #872.⁵

The sample size calculations assume that the unit of analysis will be the eye and that the outcomes from each subject's eyes will be independent.

Sample size calculations were completed using nQuery software, Version 9.

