- In order to ensure that the Investigator and site staff remain masked to the study lens, an unmasked designee at each site will be responsible for all study materials accountability, including dispensation and collection of study supplies to subjects.
- Subjects are to be instructed not to discuss or show the dispensed study lenses to the Investigator or masked site staff during the study.
- Subjects will be instructed that other contact lenses (other than the assigned study lenses) and contact lens care products (other than any eye drops provided) are not allowed to be used during the study.

Study Duration of Treatment:

Approximately 3 months

Criteria for Evaluation:

The primary endpoints are as follows:

• Effectiveness:

- o Overall comfort averaged over all scheduled follow-up visits
- o Vision averaged over all scheduled follow-up visits
- \circ The proportion of eyes with a maximum degree of front surface deposits grade of ≤ 2 over all scheduled follow-up visits

• Safety:

 \circ The proportion of eyes with any slit-lamp findings greater than Grade 2 over all follow-up visits

Statistical Methods:

- Continuous variables will be summarized using the sample size, mean, standard deviations, median, minimum, and maximum. Categorical variables will be summarized using frequencies and percentages.
- Each primary endpoint will be evaluated statistically using a one-sided non-inferiority test with a one-sided alpha risk of 0.025. For overall comfort and dryness, each non-inferiority hypothesis will be tested using an analysis of variance model including the fixed factors of treatment, site, and lens group with a non-inferiority margin of -5 points. For front surface deposits, the non-inferiority hypothesis will be tested using a one-sided Newcombe-Wilson 97.5% lower confidence limit with a non-inferiority margin of -10%. For slit-lamp findings, the non-inferiority hypothesis will be tested using a one-sided Newcombe-Wilson 97.5% upper confidence limit with a non-inferiority margin of 5%.

Sample Size Calculations:

Approximately 30 Test group subjects will be completed for each lens group in the table of lens types above. For each lens type, the probability of observing at least one subject-level event will be 0.95 when the probability of an event is 0.1. When the sample size is 150 subjects in each treatment group, the overall power of the trial will be 95%. To allow for losses of up to 10%, approximately 340 subjects (680 eyes) will be enrolled.

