8.3.1 Overall Comfort

When the sample size in each group is 300 eyes (150 subjects), a two-group one-sided 0.025 significance level t-test will have 99% power to reject the null hypothesis that the test is not non-inferior to the standard (the difference in means, μ T- μ S, is -5 or farther from zero in the same direction) in favor of the alternative hypothesis that the Test is non-inferior, assuming that the expected difference in means is 0 and the common standard deviation is 13.264.

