8.3.6 Overall Power

If the four primary endpoints are independent, then the overall power of the study is 99% x 99% x 99% x 99% = 96%.

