8.4 Randomization

An unmasked statistician who is not otherwise involved in the trial will create the randomization schedule.

Each subject will be randomized to one of the treatment arms in a 1:1 ratio (Test to Control). Randomization will be managed using a RTSM system. The randomization will be stratified by lens group and investigational site.

Efforts will be made to enroll subjects in at least three of the lens strata within each site to minimize confounding between site and lens group. While the target enrollment for each lens group is approximately 68 subjects, some lens strata may be difficult to enroll.

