8.5 Study Populations

8.5.1 Intent-to-Treat (ITT) Population

The ITT Population will consist of all randomized subjects for subject level summaries and, for eye level summaries, both of their eyes. Subjects will be included in ITT Population summaries according to the treatment group to which they were randomly assigned.

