8.6 Statistical Analysis

8.6.1 Methods of Analysis

8.6.1.1 General Methods

Continuous data will be summarized using sample size (n), mean, standard deviation (SD), median, minimum, and maximum. Categorical data will be presented using the total counts for each category and corresponding percentages. The denominator for each percentage will be the number of subjects or eyes with non-missing data unless otherwise indicated.

As is customary for contact lens solution trials, eyes will be treated as independent sampling units in eye level analyses unless otherwise noted.

Listings of data will be produced in addition to tables of summary statistics.

8.6.1.2 **Overall Comfort**

At each follow-up visit, overall comfort will be assessed for each eye on a scale from 0 to 100, with 100 denoting the most favorable response. For each eye, mean overall comfort over all follow-up visits will be computed as the average of the non-missing values over all scheduled follow-up visits. Missing data will not be imputed for the primary analysis. Mean overall comfort over all follow-up visits will be summarized at the eye level by treatment using continuous summary statistics for the ITT Set in a table. A one-sided lower 97.5% confidence limit around the difference in means between the Test and Control treatment groups, computed using an analysis of variance model including the fixed factors of treatment, site, and lens group will be displayed. If the lower confidence limit is greater than -5.0, then the null hypothesis that the test solution is not noninferior will be rejected, and the test solution will be statistically successful in this outcome.

As a sensitivity analysis, the PP Population will be analyzed for this endpoint.

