## 2.2. Sample Size Determination

Estimates of standard deviations and proportions were obtained from Bausch + Lomb Study #872.

The sample size calculations assume that the unit of analysis will be the eye and that the outcomes from each subject's eyes will be independent.

Sample size calculations were completed using nQuery software, Version 9.

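### The stated power (99% per endpoint, 96% overall) treats a subject's two eyes as independent; at moderate or high between-eye correlation that power and the one-sided 0.025 cannot both hold.

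*Protocol*

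**What the plan says.** Protocol 8.3 and SAP 2.2 take the eye as the unit: the calculations "assume that the unit of analysis will be the eye and that the outcomes from each subject's eyes will be independent". Protocol 8.3.1 then states for comfort: "When the sample size in each group is 300 eyes (150 subjects), a two-group one-sided 0.025 significance level t-test will have 99% power". Protocol 8.3.2 to 8.3.4 give the same 99% for vision, front surface deposits and slit-lamp findings, each with 300 eyes per arm. Protocol 8.3.6 multiplies them: "If the four primary endpoints are independent, then the overall power of the study is 99% x 99% x 99% x 99% = 96"%. SAP 2.2.7 repeats this. The synopsis differs: "When the sample size is 150 subjects in each treatment group, the overall power of the trial will be 95"%.

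Protocol 8.4 randomises subjects, not eyes. The ITT definition in 8.5.1 brings both eyes of each subject into eye-level summaries. For the analysis, Protocol 8.6.1.1 states that "eyes will be treated as independent sampling units in eye level analyses unless otherwise noted", calling this customary for such trials. SAP 4.1 and 4.5.2 carry the same rule into the four primary analyses. Neither document gives a between-eye correlation or a design effect. The sensitivity analyses in SAP 4.5.3 (per-protocol, best/worst-case imputation, tipping point) do not address pairing.

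**The concern.** The two eyes of a subject share the person, the assigned solution and the lens brand (inclusion criterion 9). Comfort and vision are 0 to 100 ratings that one person gives for both eyes. Zero correlation is therefore hard to defend for a comparison made between subjects.

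With positive correlation, the variance of a difference between arms is larger than the eye-level formula says. Either the analysis allows for this and loses power, or it does not and exceeds 0.025. The trial succeeds only if all four endpoints succeed, so small losses multiply. One of the four is the primary safety endpoint, where excess type I error means accepting a solution at the 5% margin too often. Someone reading 96% overall power at one-sided 0.025 cannot tell which of the two properties is being given up.

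**Working it through.** **Inputs.** One-sided alpha 0.025 (synopsis); 300 eyes, 150 subjects per arm; true difference 0. Comfort: SD 13.264, margin -5 (8.3.1). Vision: SD 11.7, margin -5 (8.3.2). Deposits: 0.942 in both arms, margin -0.10 (8.3.3). Slit-lamp: 0.008 in both arms, margin 0.05 (8.3.4). Rho is not in the documents and is varied from 0 to 1. Products assume independent endpoints, as the plan does.

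**1. The plan's figures at rho = 0.** Comfort: SE = 13.264 x sqrt(2/300) = 1.083; 5/1.083 = 4.617; Phi(4.617 - 1.96) = 99.6%. Vision gives 99.9% in the same way. Exact binomial enumeration of the Newcombe-Wilson limits gives 99.9% for deposits and 99.9% for slit-lamp. The stated 99% figures are met, and 0.99^4 = 96.1%. The product of the unrounded powers is 99.4%, so there is some reserve.

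**2. Power with alpha held at 0.025.** With two eyes per subject the design effect is 1 + rho, so effective n per arm = 300/(1+rho). Means use the non-central t; proportions use Newcombe-Wilson at effective n rounded to 231, 200, 167 and 150. Example, comfort at rho 0.5: n = 200, SE = 13.264 x sqrt(2/200) = 1.326, power 96.4%.

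| rho | comfort | vision | deposits | slit-lamp | overall |
|---|---|---|---|---|---|
| 0.3 | 98.1% | 99.6% | 99.2% | 99.4% | 96.4% |
| 0.5 | 96.4% | 98.9% | 98.1% | 97.5% | 91.2% |
| 0.8 | 92.9% | 97.3% | 96.0% | 94.0% | 81.6% |
| 1 | 90.2% | 95.8% | 93.4% | 91.3% | 73.7% |

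Comfort falls to 99% at rho 0.156. Overall power is 95.3% at rho 0.35. Applying the design effect without rounding n gives 96.1%, 91.4%, 82.4% and 73.7% overall, so the first decimal should not be leaned on.

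If all 170 randomised subjects per arm contribute data (n = 340/(1+rho)), overall power is 98.3%, 95.6%, 89.5% and 82.3% at the same four values.

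**3. The planned eye-level tests, 150 subjects per arm.** For means, power = Phi((5/SE - 1.96)/sqrt(1+rho)) with SE at 300 eyes, and true error at the margin = 1 - Phi(1.96/sqrt(1+rho)). Example at rho 0.5: comfort power Phi(2.657/1.225) = 98.5%; error 1 - Phi(1.600) = 0.055. For proportions, the exact distribution of 150 correlated eye pairs per arm was used, with error evaluated at 0.842 vs 0.942 and at 0.058 vs 0.008.

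| rho | overall power | error, comfort and vision | error, deposits | error, slit-lamp |
|---|---|---|---|---|
| 0.3 | 98.2% | 0.043 | 0.043 | 0.039 |
| 0.5 | 97.1% | 0.055 | 0.056 | 0.051 |
| 0.8 | 95.0% | 0.072 | 0.074 | 0.070 |
| 1 | 93.3% | 0.083 | 0.086 | 0.077 |

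A simulation of 40,000 trials per scenario agrees for the means: for comfort at rho 0.5 the eye-level test had error 0.056 and power 98.5%, and a subject-level test 0.026 and 96.5%.

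**The case against.** The independence assumption is disclosed, and under it the stated figures are conservative. Rho is unknown to us, so what is shown is a conditional risk and not a demonstrated shortfall. For the tests actually planned, overall power stays at or above 96% up to rho of about 0.65; the figures of 91% and lower belong to an analysis the plan does not contain. On this view the defect lies mainly in the analysis method. In addition, site and lens group in the ANOVA may reduce the residual SD and correlation. As an illustration, a 10% smaller SD would lift comfort power at rho 0.5 from 96.4% to 98.7%. Finally, the inflated error matters for the overall decision mainly when a product sits near one margin and passes the other three.

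Most of this is fair and limits the claim, but it does not remove it. Disclosure does not supply a value for rho. The planned tests keep their power only by exceeding the 0.025 that the same sentences promise. The effect of site and lens group cannot be quantified from the documents. Requiring all four endpoints does not restore 0.025, because the worst-case error of the joint rule is that of a single endpoint.

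**Conclusion.** The concern holds, as a conditional statement about power and alpha together. The arithmetic under independence is sound, and its reserve protects the overall 96% up to rho of about 0.30 and comfort's 99% up to about 0.15 with alpha held at 0.025. Beyond that the two claims conflict. At zero true difference and 150 subjects per arm, the chance of missing at least one endpoint, against the stated 4%, is:

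- with alpha held: 3.6%, 8.8% and 18.4% at rho 0.3, 0.5 and 0.8;
- with the planned tests: 1.8%, 2.9% and 5.0%, while a product exactly at a margin passes that endpoint roughly 4%, 5% and 7% of the time instead of 2.5%.

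These sizes rest on an assumed rho common to all endpoints, independent endpoints, and the Study #872 SDs and proportions. The 95% versus 96% mismatch needs no assumption; it is editorial.

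**What to change.** In the synopsis, Protocol 8.3.1 to 8.3.6 and SAP 2.2.1 to 2.2.7, restate power with effective n = 300/(1+rho), taking rho per endpoint from the eye-level data of Study #872, already the source of the SDs and proportions. If rho cannot be obtained, show the range down to 150 per arm. Say that these figures apply to an analysis that accounts for eyes within subject, and quote one overall figure everywhere.

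Make the primary analyses match (Protocol 8.6.1, SAP 4.5.2). For comfort and vision, add a subject random effect or subject-clustered robust variance to the ANOVA. For the two proportions, use a clustered interval such as Newcombe-Wilson at effective n. Slit-lamp events are too few to estimate rho in this trial (300 x 0.008 = 2.4 eyes per arm), so either prespecify rho or use the number of subjects. Prespecifying is cheaper: with n = 150 for slit-lamp alone, overall power is 88.5%, 85.4% and 79.2% at rho 0.3, 0.5 and 0.8.

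The cost is a rerun of the calculation, text edits, and an amended variance method for four analyses before unmasking, which Protocol 8.0 allows if documented. Stated power becomes less favourable: at rho 0.5 and 150 per arm, the chance of success at zero true difference falls from about 97% to 91% with rho prespecified. No change to enrolment is proposed.
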